2.6 Other sources of bias (avoiding detection bias)

Group allocation will be concealed from the woman and the ward staff, although blinding in theatre is not possible given this is a surgical trial. Women will not be informed after their surgery of the procedure actually carried out unless they specially request this information. Outcome assessment is largely by participant self-completed questionnaire, so avoiding interviewer bias. The clinical review at 12 months in Outpatients will be conducted by research staff blinded to allocation rather than the clinical staff caring for the woman. Randomised participants will undergo an objective vaginal POP-Q assessment without the operator having knowledge of the group allocation. Women and research staff will not be explicitly informed of which operation was randomly selected, although examination may reveal which operation was actually carried out.

A researcher who is blinded to allocation will conduct the data collection, data entry and analysis, using Study Numbers only to identify women and questionnaires. In the RCTs, all women will be actively followed up with analysis based on the intention-to-treat principle. All analyses will be clearly predefined to avoid bias.

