All randomised participants will have a review appointment with an appropriately qualified Recruitment Officer and, if necessary, their gynaecologist, at 12 months to evaluate the results of surgery and identify problems or a need for other treatment. In some sites, this amounts to more postoperative surveillance than is available routinely in the NHS, and should ensure that women receive optimum care.

2.3 Randomisation and allocation to management group for women who consent to be randomised (avoiding selection bias)

When contact details, essential baseline information and confirmation of signed consent are entered into the internet based PROSPECT database, the local researcher will be able to randomise the woman (if appropriate) to one of the groups for which she is eligible (see Flow Diagram, Appendix II). Randomisation will be carried out as close to the time of surgery as is practical (either on the morning of the operation or the previous afternoon), taking into account the hospital routines and time needed for setting up the operating theatre.

Randomisation will utilise the existing proven remote automated computer randomisation application at the study adminstrative centre in the Centre for Healthcare Randomised Trials (CHaRT, a fully registered UK CRN clinical trials unit) in the Health Services Research Unit, University of Aberdeen. This randomisation application will be available both as a telephone-based IVR system and as an internet based service.

Randomisation will be computer-allocated and stratified depending on whether a woman is having a primary or secondary repair.

Primary prolapse (de novo) is defined as a prolapse in a compartment that has not previously been repaired. If the woman is having two primary procedures (i.e. both anterior and posterior vaginal wall prolapses require repair), the randomised allocation will be applied to both prolapse repairs.

Secondary prolapse is defined as a recurrence of prolapse after a previous procedure, when the recurrence is in the **same** compartment. If the woman also needs a concomitant primary repair of a de novo prolapse in a different compartment, this procedure will be chosen on clinical grounds (i.e. not dictated by the randomisation allocation for the secondary procedure).

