4 SUBSEQUENT ARRANGEMENTS

4.1 Informing key people

Following formal trial entry:

The Study Office will:

i) inform the woman's General Practitioner (by letter enclosing information about PROSPECT and Study Office contact details.

The local Recruitment Officer will:

- i) file the Hospital Copy of the Consent form in the hospital notes along with information about PROSPECT and the POP-Q measurements.
- ii) inform the ward and theatre staff as appropriate of the woman's entry to the study and details of the intervention allocation (theatre only).
- iii) use the PROSPECT internet database to enter data regarding the participant, including data required to complete randomisation; and intra-operative and postoperative information abstracted from local medical records.
- iii) return all study documentation to the Study Office in Aberdeen after database entry of essential data.

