Woman-reported outcomes will be assessed by participant-completed questionnaires in hospital after surgery and at home at 6, 12, 18 and 24 months. Gynaecologists, supported by Recruitment Officers, will complete a questionnaire at the time of surgery providing details of the operative procedures, complications and resource use, and a short clinical questionnaire at the 12 month outpatient review appointment including a POP-Q measurement.

Economic outcomes will be assessed using standard economic methods plus study-specific data collection described earlier. The standardised outcome instruments developed by the International Consultation on Incontinence (ICI)⁹ for urinary and bowel function will be used. We will use the International Continence Society (ICS) recommendations for terminology and standard techniques.¹⁰ Consumer groups and our Consumer Advisor will contribute to ensuring that all relevant issues are covered, the patient information and survey instruments are acceptable to the women and the outcome measures relevant.

The ways in which these data will be analysed are set out in the PROSPECT Statistical Analysis Plan and Dummy Tabulations.

It is anticipated that the data generated by the study, along with other focused data collection sets, may be used as a basis for exploratory or epidemiological research, but these will be described in separate protocols.

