- use this information to randomise the women using the web-based PROSPECT database or the linked telephone randomisation service
- ensure operative and postoperative data are collected and recorded in the web-based PROSPECT database or the BSUG database as appropriate, and send paper copies to the Study Office
- file relevant study documentation (eg consent forms, POP-Q results) in the woman's medical records
- organise and supervise alternative recruiters in case of holiday or absence
- represent the centre at the collaborators' meetings.

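### The protocol calls the 12-month POP-Q review blinded, but no procedure keeps the allocation from the examiner

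*Protocol*

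**What the plan says.** Section 2.6 of the protocol makes three statements about the assessor. On the visit: "The clinical review at 12 months in Outpatients will be conducted by research staff blinded to allocation rather than the clinical staff" (meaning those caring for the woman). On the measurement, the POP-Q is to be made "without the operator having knowledge of the group allocation". On information in general: "Women and research staff will not be explicitly informed of which operation was randomly selected", with one reservation, "although examination may reveal which operation was actually carried out".

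Other sections hand out the tasks:

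- Section 2.2: "All randomised participants will have a review appointment with an appropriately qualified Recruitment Officer", with the woman's own gynaecologist joining if needed.
- Section 2.4: trained Recruitment Officers, not staff responsible for the woman's care, must see that the POP-Q is done and independently recorded, both before surgery and at 12 months in randomised women. The surgeon, the officer or both may complete the Theatre Questionnaire.
- Section 8.1: the officer's duties include to "use this information to randomise the women using the web-based PROSPECT database or the linked telephone randomisation service".
- Section 4.1: the officer tells ward and theatre staff that the woman is in the study and gives "details of the intervention allocation (theatre only"). The officer also enters operative information taken from the notes.
- Section 6.2: gynaecologists, helped by officers, complete "a short clinical questionnaire at the 12 month outpatient review appointment including a POP-Q measurement".
- Section 8.4.4: the gynaecologist and theatre staff cannot be blind once randomisation has taken place.

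The SAP does not mention assessor blinding.

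**The concern.** Section 2.6 presents blinding of the examiner as a property of the design, yet both roles named for the 12-month assessment hold the allocation under other sections.

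Several results depend on this visit. POP-Q stage at the operated site and de novo prolapse elsewhere are listed secondary outcomes (protocol 6.2, SAP Secondary Outcomes). Appendix IV says the examination was meant to identify treatment success and adverse effects. The planned comparison of patient-reported with clinician-observed outcomes (protocol 6.4, SAP Methodological analyses) uses the same data.

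Under Appendix III, POP-Q points are read to the nearest centimetre while the woman strains, and the stage boundaries near the hymen turn on 1 cm. An examiner who expects mesh to hold better, or to do harm, could lean either way on a close reading. If the results were then reported as blinded, readers would trust them more than the procedures justify.

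**Working it through.** No arithmetic decides this point. The check is to set each task beside the role that performs it and ask whether that role learns the allocation.

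| Task | Role | Protocol section | Does the role learn the allocation or operation? |
|---|---|---|---|
| Randomise the woman | Recruitment Officer | 8.1 | Yes, unless the system hides the result, which no text says |
| Tell theatre the allocation | Recruitment Officer | 4.1 | Yes |
| Enter operative data from the notes | Recruitment Officer | 4.1 | Yes, the operation performed |
| Theatre Questionnaire | Surgeon and/or Recruitment Officer | 2.4 | Yes, for whoever completes it |
| 12-month review appointment | Recruitment Officer; gynaecologist if needed | 2.2 | Claimed blind in 2.6 |
| Ensure 12-month POP-Q is done and recorded | Recruitment Officer | 2.4 | Claimed blind in 2.6 |
| Complete 12-month form with POP-Q | Gynaecologist, supported by officer | 6.2 | Gynaecologist cannot be blind (8.4.4) |

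1. The officer must have the allocation in order to pass it on. The theatre-only limit in Section 4.1 keeps it from ward staff, not from the officer.
2. The same role carries the 12-month review and the POP-Q. No sentence in either document requires the examiner to be someone other than the person who randomised the woman or handled her theatre data.
3. Section 6.2 conflicts with Sections 2.4 and 2.6. It has gynaecologists complete the POP-Q without condition, whereas 2.4 gives responsibility to research officers and 2.6 excludes the treating clinical staff. Section 2.2 brings in the gynaecologist only if needed. The sections do not agree on who examines.
4. The reservation in Section 2.6 covers unblinding through what the examiner sees. It does not cover an examiner who held the allocation before the visit.
5. Number in scope: Appendix IV gives 1353 women randomised in the primary trial and 155 in the secondary trial, so 1353 + 155 = 1508. This is a ceiling. It counts women randomised, not women examined, and not women examined by someone who knew their allocation.

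**The case against.** The strongest reply is that the conflict is between roles, not persons. One bullet in Section 8.1 allows for more than one officer at a centre, another provides for alternative recruiters, and Section 2.3 refers only to a local researcher as the person who randomises. Section 2.4 asks for independent recording. A centre could therefore have kept its examiner blind while following the protocol. This stands, and it rules out saying that blinding is impossible. It does not rescue the claim in Section 2.6, because what a site may arrange is not what the protocol requires.

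The gynaecologist's part may also be smaller than it looks. Section 2.2 makes it conditional, and Section 6.2 does not say that the gynaecologist is the woman's own. That also stands: Section 6.2 may be a loose sentence. It still contradicts two other sections and needs correcting.

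There are real safeguards. Staff are trained, and the POP-Q is measured with rulers under set conditions. These limit the room for bias without removing it. Some unblinding is unavoidable in any case, since mesh exposure seen at examination itself reveals mesh, and Section 2.6 admits as much.

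**Conclusion.** The concern holds in this form: the protocol claims a blinded 12-month examiner, and no procedure secures it. POP-Q stage at the original site, de novo prolapse and the other 12-month clinical findings are open to detection bias in either direction.

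A reader might infer more than the documents support:

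- That the assessor was necessarily unblinded. The texts assign roles and leave room for a different individual at 12 months.
- That most or all of the 1508 women were examined by the person who randomised them. Neither document gives the number of officers per centre or says who performed each review, so the number is unknown.
- That the bias can be sized against the anterior relapse rates in Appendix I. Those rates come from other trials, neither document states an expected POP-Q difference for this one, and nothing indicates how often knowledge of the allocation would change a reading. Any figure would be invented.
- That the main result is compromised. The POP-SS is self-completed by women who are not told their operation unless they ask, so it is not directly affected.

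This is a point about secondary outcomes, to be settled in the protocol text, the SAP and the reporting.

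**What to change.** 1. Reconcile Sections 2.2, 2.4, 2.6, 4.1, 6.2 and 8.1. Where a site has more than one trained officer, state that the 12-month POP-Q is done by one who neither randomised the woman nor handled her theatre data. Remove gynaecologists as completers of the POP-Q in Section 6.2, and make clear that their conditional attendance under Section 2.2 is not for recording it.
2. Record for each examination whether the examiner randomised the woman or knew her operation beforehand. Use a tick-box at any reviews still to come, and the randomisation, theatre and review records for those already done.
3. Pre-specify in the SAP a sensitivity analysis of the POP-Q outcomes restricted to examinations without prior knowledge, using the same model as the main analysis. Report the numbers retained in each arm, because the restriction is defined after randomisation.
4. Do not describe the 12-month assessment as blinded, in Section 2.6 or in reports, where this cannot be shown.

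Rerouting the release of allocations would not be enough. Recruitment closed in August 2013 (Appendix IV; SAP Study Design), so it could not act on women already randomised. Even before then, the officer would still have met the operation while abstracting theatre data. If all reviews are complete, item 1 can only correct the text, and items 2 to 4 carry the remedy.

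The cost is one extra data item, one additional analysis and a more modest blinding claim. The restricted analysis will have fewer women, perhaps few if most examiners had prior knowledge. That would itself be worth reporting.

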2.7 Sample size and feasibility

2.7.1 Feasibility study

In 2006 a pilot RCT was carried out in one centre (Aberdeen) to test the methods, practical arrangements and feasibility of use of mesh in women having prolapse surgery. IMPRESS (Insertion of Mesh or sutures for PRolapsE Surgery Success) was a 2x2 factorial design RCT of mesh versus no mesh, and polydioxanone versus polyglactin sutures. We have now carried out a two-year follow up (IMPRESS). We found that the primary outcome, the patient-reported Pelvic Organ Prolapse-Symptom Scale (POP-SS) improved by 9 units from baseline to 6 months after surgery (94% response), and this was largely maintained at 2 years (83% response).

This trial forms the template for this study. Very few women were unwilling or unsuitable to be randomised (7%) in the pilot but we have used a much more conservative estimate of 50% in the sample size calculations because the proposed trial includes a more radical mesh option (which women and gynaecologists may not wish to choose) and because in a UK-wide multicentre trial, there may be more variation in uptake between centres.

Women who are not suitable or who do not wish to be randomised will be followed up in the same manner as the randomised women, with supplementary information on the reasons for non-randomisation, in the Comprehensive Cohort Study design.

2.7.2 Sample size sought

In an average population of women having prolapse surgery, about 70% will be having a primary procedure. In the current RCT amongst these women, two comparisons will be made:

- a standard repair versus a standard repair using a biological graft inlay; and
- 2. a standard repair versus a standard repair using a non-absorbable or combined mesh inlay.

Pilot data have shown that a conservative estimate of the standard deviation of the primary patient-reported outcome POP-SS is 8 units. A difference in means of 2 units would represent an improvement in the response to a POP-SS question, for example, a feeling of something coming down or in the vagina, from 'Most of the Time' to 'Occasionally'. To detect a standardised difference of 0.25 with 90% power and alpha equal to 0.025 (to maintain the nominal p value at 0.05 with two tests being used), we would need to randomise 400 women to each arm of the study. Best efforts using evidence based techniques will be employed to maximise the response rate at follow up. Nevertheless, we feel it prudent to inflate the estimated sample size for 15% dropout at one year requiring approximately 1450 women having primary surgery to be recruited to the trial. Adjusting for baseline covariates and minimising the loss to follow up will potentially improve this power. A trial of this size would also be adequately powered to detect important differences in the economic and secondary outcomes.

It is estimated that the other 30% of women requiring anterior and/or posterior repair will receive a secondary or subsequent repair. Therefore, during the proposed time period required for recruiting 1450 women to the primary repair RCT above, it is anticipated approximately 620 women having secondary surgery will be eligible and will be willing to be randomised.

Within the secondary RCT two comparisons will be made:

- 1. a standard repair versus a standard repair using a non-absorbable or combined mesh inlay; and
- 2. a standard repair versus a mesh kit procedure.

It would be possible to detect with 90% power and alpha equal to 0.025 a standardised effect size of 0.38 which equates to 3 points on the POP-SS scale (this estimated effect detectable has been calculated adjusting for potential 15% dropout at one year). The pilot data from IMPRESS indicated that women having secondary repairs have a higher level of symptoms at baseline. Therefore it is biologically plausible that these women may show a larger benefit from the options available.

Thus 2070 women will be randomised in total. Based on data from the feasibility study, we expect that in a typical centre, 200 women a year will be eligible, of whom 50% will be willing to be randomised. Of these women, 70% will be having primary surgery, 30% will have both anterior and posterior surgery, 15% may have a concomitant continence procedure and 30% a concomitant upper vaginal procedure (e.g. cervical amputation or vaginal hysterectomy). More than 15 centres are willing to take part.

If we conservatively assume 50% of the women will agree to be randomised, we calculate we will need the equivalent of 18 months full time recruitment to randomise 2070 women and will follow up 4140 women in total including those in the Comprehensive Cohort. Allowing for about another 10% who will not wish to be studied in any way, we will need to approach around 4500 women.

Allowing for a staggered start, with the inception of the trial in the three centres led by the co-applicants, then rolling out to the other centres, this recruitment will take place over 30 calendar months. We have collected recent information from the

participating centres to give robust reassurance of the feasibility of these recruitment estimates and their willingness to participate. The centres are in: Aberdeen, Manchester, Plymouth, Liverpool, Croydon, Basingstoke, London (Homerton), Leeds, Glasgow (Southern General, Victoria), Stirling, Rotherham, Leicester, Birmingham, York, Hull, Nottingham, Gwent, Bradford, Blackburn, Dundee, Middlesborough and Bristol.

Table 1 Recruitment numbers expected

	Primary	Secondary	Non-randomised
	procedure	procedure	cohort
	(randomised)	(randomised)	N=2070
	N=1450	N=620	
Women needed per arm (minimum)	400	175	
Allowing for 15% dropout	483	206	
Total N of women	1450	620	2070
Assuming 50% willing to enter RCT, N. women having prolapse surgery needed	2900	1240	2070
No. of operations per year per typical centre	70	30	100
No. of typical centres needed for approx 18 months		15	

Allowing for 10% of women who will not wish to take part in the study at all, it is anticipated that 4500 women will need to be screened in order to achieve the recruitment rates required.

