1.2 The questions which this study will address

Principal Objectives

To determine the effectiveness (including safety) and cost-effectiveness of surgical treatment, primarily in terms of improvement in prolapse symptoms, in women having anterior and/or posterior vaginal wall pelvic organ prolapse surgery, in two groups:

(A) In women having a primary prolapse repair, the effects of:

- 1) a standard repair versus a standard repair using a biological graft inlay; and
- 2) a standard repair versus a standard repair using a non-absorbable or combined mesh inlay.

(B) In women having a secondary prolapse repair, the effects of:

- 3) a standard repair versus a standard repair using a non-absorbable or combined mesh inlay; and
- 4) a standard repair versus a mesh kit procedure.

The two groups are being considered independently because different surgical options are considered to be appropriate for clinical reasons.

Secondary Objectives

- to determine the differential effects on other outcomes such as urinary, sexual and bowel function, quality of life, general health, need for secondary surgery and adverse effects;
- to identify possible effect modifiers (eg different types of mesh, concomitant procedures, age, complex prolapse types);
- 7) to establish if the findings of the research, including implications for service delivery, training and introduction of mesh, are generalisable to the NHS.

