Because of the importance of mesh in (theoretically) reducing the repeat surgery rate, we further propose that an additional primary clinical outcome will be the rate of repeat surgery for prolapse (any compartment). For repeat prolapse surgery within 14 years, if the event rate for the standard midline repair is assumed to be 25%, the power to detect a 10% absolute difference in reoperation rates compared with either biological or synthetic mesh would be 90% if the current response rate was maintained and 66% if the response rate falls to 50%.

The primary economic outcome measure of cost effectiveness will remain the same: the incremental cost per QALY (QALYs based on the EQ-5D⁶). In addition, because of all the potential problems associated with the use of mesh in prolapse surgery, serious adverse events will be included as a secondary outcome.

Following completion of the 14 year dataset, the full trial data will be reported for the randomised and the corresponding comprehensive cohort according to the trial

Statistical Analysis Plan. Analyses related to the two randomised trials (primary and secondary surgery) will be undertaken on an intention-to-treat basis allowing for repeated (two-yearly) symptom and quality of life measurements. Data from Cohort women will be analysed according to treatment received (mesh or no mesh surgery), separately according to primary or secondary procedure, or upper vaginal prolapse surgery only.

[figure not shown]
Management

Trial management, data collection and analysis will be undertaken in the PROSPECT Trial Office, HSRU, University of Aberdeen, under the supervised of the PROSPECT Project Management Group. This group consists of the grant holders and representatives from the Study Office.

References

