## **Statistical Methods**

### **General Methods**

The statistical analysis of the RCTs will be based on all women as randomised, irrespective of subsequent compliance with the treatment allocated (intention to treat). The principal comparisons will be:

- In women having a primary prolapse repair,
  - a standard anterior and/or posterior repair will be compared with a standard repair using a biological graft inlay; and
  - a standard anterior and/or posterior repair will be compared with a standard repair using a non-absorbable or combined mesh inlay.
- In women having a secondary prolapse repair,
  - a standard anterior and/or posterior repair will be compared with a standard repair using a non-absorbable or combined mesh inlay; and
  - a standard anterior and/or posterior repair will be compared with a mesh kit procedure using an introducer device.

The two trials are being considered independently because different surgical options are considered to be appropriate for clinical reasons. Women who are not randomised but who are in the Comprehensive Cohort group will be analysed according to the operation actually carried out.

Descriptive statistics will be tabulated by treatment allocation for all outcomes (mean and SD for continuous data, proportions for binary data). Treatment effects will be estimated with 95% confidence intervals for all outcomes (mean differences for continuous data, odds ratios for binary data). Statistical significance will be at the 5% level and corresponding confidence intervals will be derived. Analyses will be conducted using SAS v9.3.

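### The unqualified claim of adequate power for secondary outcomes does not hold for uncommon harms, nor for 24-month reoperation if event rates are low

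*Protocol*

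**What the plan says.** The primary trial was sized on one outcome, the POP-SS at one year. Protocol 2.7.2 says "a conservative estimate of the standard deviation of the primary patient-reported outcome POP-SS is 8 units" and takes a difference of 2 units as the target. The stated design is "To detect a standardised difference of 0.25 with 90% power and alpha equal to 0.025", from which "we would need to randomise 400 women to each arm of the study". The plan then proposes to "inflate the estimated sample size for 15% dropout at one year requiring approximately 1450 women". The paragraph ends with the claim at issue: "A trial of this size would also be adequately powered to detect important differences in the economic and secondary outcomes". The SAP section on sample size and power repeats it word for word.

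The secondary outcomes it covers (Protocol 6.2; SAP, Secondary Outcomes) range from anatomical prolapse stage to organ injury, transfusion, sepsis, mesh removal and further surgery. Safety is part of the principal objective: "To determine the effectiveness (including safety) and cost-effectiveness of surgical treatment" (Protocol 1.2).

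The SAP (General Methods) reports all treatment effects with 95% confidence intervals, using odds ratios for binary data, and adds: "Statistical significance will be at the 5% level and corresponding confidence intervals will be derived".

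The only power calculation for a binary outcome is in Protocol Appendix IV, for repeat surgery within 14 years. With 25% assumed after standard repair, "the power to detect a 10% absolute difference in reoperation rates compared with either biological or synthetic mesh would be 90" (per cent) if the current response rate is maintained, and 66% if it falls to half.

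**The concern.** A sample size chosen for a mean difference on a symptom score says little about power for a proportion of 1% to 5%. The sentence makes no distinction between common and uncommon outcomes, and nothing in either document supports it for the uncommon ones. The one binary calculation that exists uses a 25% event rate accumulated over 14 years, whereas main-study follow-up ends at 24 months (Protocol section 5).

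What is at stake is interpretation. A reader told that the trial had adequate power for its secondary outcomes may take a non-significant odds ratio for organ injury, or for reoperation at two years, as evidence against an important difference. Neither document sets a margin or an upper limit for excess harm that would guard against this.

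**Working it through.** **1. The plan's own figures.** All of them reproduce.

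- POP-SS: n per arm = 2(z₀.₉₈₇₅ + z₀.₉₀)²/d² = 2(2.241 + 1.282)²/0.25² = 397.2, so 398, against 400 stated. Alpha is therefore two-sided 0.025 per comparison.
- Dropout: 400/0.85 = 471 per arm; 471 × 3 = 1413, against about 1450 stated (483 per arm in Table 1).
- Appendix IV reoperation, 25% v 15%, alpha 0.025, normal approximation: 90.4% at 400 per arm (stated 90%) and 66.0% at 225 per arm (stated 66%).

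**2. Method for the secondary outcomes.** The test is the pooled two-proportion z-test. Power is exact: the binomial probabilities of all pairs of event counts that give |z| above the critical value are summed. As a check, 25% v 15% at 400 per arm and alpha 0.025 gives 91%. Alpha is shown at 5% (SAP, General Methods) and 2.5% (the sample-size calculation).

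**3. A common outcome.** Anatomical relapse at the rates in Protocol Appendix I, 1.2.2 (30% without mesh, 14% with any mesh): over 99% at 400 per arm.

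**4. Uncommon harms.** The documents give no comparator rates, so a range of assumed base rates is used, each doubled.

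| Rates | 400 per arm, 5% | 400 per arm, 2.5% | 483 per arm, 5% |
|---|---|---|---|
| 1% v 2% | 19% | 13% | 23% |
| 2% v 4% | 38% | 27% | 45% |
| 3% v 6% | 54% | 43% | 62% |
| 4% v 8% | 67% | 56% | 75% |
| 5% v 10% | 78% | 68% | 85% |

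The 483 column covers theatre and first-week events, which one-year dropout need not affect. Fisher's exact test would be lower: 13%, 32% and 48% for the first three rows at 400 per arm and 5%.

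Absolute size matters as well as the ratio. At 400 per arm and 5%, 2% v 5% has 65% power and 1% v 4% has 81%.

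**5. Reoperation at 24 months.** No rate is given, so two assumptions are shown.

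- Constant hazard: 1 − (1 − 0.25)^(2/14) = 4.0% and 1 − (1 − 0.15)^(2/14) = 2.3%. Power is 29% (19% at alpha 2.5%). About 1602 women per arm would be needed for 80% power at 5%.
- Early reoperations, keeping the same ratio (15/25 = 0.6): 8% v 4.8% gives 46% (35%); 10% v 6% gives 55% (44%).

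**6. Width of the interval.** If both arms have the same observed rate p, the 95% half-width for the risk difference is 1.96√(2p(1 − p)/400): 1.4 points at 1% and 1.9 points at 2%. Identical observed rates of 1% would thus leave a doubling within the interval. At 2% the interval would reach almost to a doubling.

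**7. Numbers actually randomised** (SAP Table 2, strata combined as planned, no losses): 253 + 178 = 431 v 256 + 181 = 437 for synthetic mesh, and 253 + 116 = 369 v 255 + 114 = 369 for biological mesh. At 5%, 2% v 4% has 40% and 36% power respectively.

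**The case against.** The strongest reply has four parts.

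- **The rates are chosen by the reviewer.** This stands as a limit. A reader might infer that the trial would miss relevant differences most of the time. The documents do not support that as a general statement: at 5% it fails for 3% v 6% (54%) and for reoperation at 10% v 6% (55%), and halving a 10% reoperation rate would have 78% power. The 2.8% organ-damage figure in Protocol Appendix I cannot fill the gap. It concerns introducer devices, used only in the secondary trial, and has no comparator.
- **Many secondary outcomes are well powered.** This also stands. It would be wrong to say that the trial is powered for POP-SS alone.
- **Nobody plans to read non-significance as safety.** Correct. A reader might infer such an intention from the sentence, but neither document states one, and the SAP already promises 95% confidence intervals for all outcomes. Misreading is a foreseeable risk, not a planned step.
- **The protocol recognises that two years is short.** Appendix IV makes repeat surgery an additional primary outcome at 14 years, with its own calculation. That calculation is sound, but it does not support a claim about 24 months.

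None of this supplies a basis for the unqualified sentence. At assumed base rates of 1% to 3%, a doubling reaches at most 62% power, even with all 483 women per arm analysed.

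**Conclusion.** The concern holds, limited to uncommon harms and to 24-month reoperation at low event rates. For a doubling from 1%, 2% or 3%, power at 400 per arm is 19%, 38% or 54% at the 5% level (13%, 27% or 43% at 2.5%), well short of the 90% used for the primary outcome. For 24-month reoperation it is 29% under constant hazard and 46% to 55% in the two early-event scenarios.

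These figures rest on assumed event rates, on reductions in reoperation in the same ratio as in Appendix IV, and on an unadjusted test. The choice between 5% and 2.5% does not change the conclusion. The sentence concerns the primary trial; the secondary trial, with 155 women randomised, is much smaller and is not covered by it. Power for the economic outcomes was not examined here.

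No stated sample size or power figure is wrong. The fault is an unsupported general claim.

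**What to change.** In Protocol 2.7.2 and in the SAP section on sample size and power, replace the sentence with:

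> The sample size was set for POP-SS. It also gives high power for large differences in common secondary outcomes, but not for uncommon ones: with 400 women per arm (two-sided 5%), power to detect a doubling is about 19% from 1%, 38% from 2%, 54% from 3% and 78% from 5%. Non-significant results for uncommon harms and for reoperation at 24 months will therefore not be interpreted as absence of a difference; they will be interpreted from the 95% CI, including the risk difference and the largest excess risk not excluded.

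This also removes the claim about economic outcomes. If the authors wish to keep it, it needs its own stated basis.

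The cost is one passage of text in two documents, plus a risk difference alongside the odds ratio for these outcomes. Design, sample size and primary analysis are unchanged. A stated property of the trial becomes less favourable.
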